8.2. Subject Exclusion Criteria

1. Subject requires supplemental oxygen delivered by mechanical ventilation, either invasive or bilevel positive airway pressure.

[figure not shown]
2. Subject admitted to Intensive Care Unit / Pulmonary Acute Care Unit designated area with severe pulmonary pneumonia, ARDS or Sepsis.
3. Subject is pregnant or breastfeeding.
4. Subject has a history of chronic asthma requiring ongoing medical therapy or other chronic pulmonary disease that, at the discretion of the treating physician, would contraindicate participation in this study.
5. Subject has any other organ dysfunction [Common Terminology Criteria for AEs (CTCAE) Version 5.0 Grade 3] that will interfere with the administration of the therapy according to this protocol.
6. Subject has inadequate organ function as defined below at time of Treatment Eligibility Period:
 - a) Subject has aspartate aminotransferase (AST), alanine aminotransferase (ALT), or alkaline phosphatase $\geq 5 \times$ the upper limit of normal (ULN). (It is anticipated that the infection may impact liver.)
 - b) Estimated glomerular filtration rate (eGFR) < 30 mL/min/1.73 m² as calculated using the Modification of Diet in Renal Disease Study equation (Levey, 2006) or history of an abnormal eGFR < 60 . A decline of > 15 mL/min/1.73 m² below normal in the past year prior to infection. (It is anticipated that the infection may impact renal function.)
 - c) Subject has a bilirubin level > 2 mg/dL (unless subject has known Gilbert's Syndrome).
7. Subject has a known sensitivity or allergy to treatment additives or diluent substances of dimethyl sulfoxide (DMSO), PlasmaLyte A or human serum albumin (HSA). Please refer to investigational brochure (IB).
8. Subject has active autoimmune disease other than controlled connective tissue disorder or those who are not on active therapy.
9. Subject is immunocompromised, has known human immunodeficiency virus (HIV) positivity, or has actively been treated with immunosuppressive products prior to being infected with SARS-CoV-2.
10. Subject has known active malignancy, unless the subject has been free of disease for ≥ 3 years from the date of signing the ICF. Exceptions include the following noninvasive malignancies:
 - a. Basal cell carcinoma of the skin
 - b. Squamous cell carcinoma of the skin
 - c. Carcinoma in situ of the cervix
 - d. Carcinoma in situ of the breast
 - e. Incidental histological finding of prostate cancer (TNM stage of T1a or T1b)

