12.1.12.1. Real-Time Reverse-Transcriptase-Polymerase-Chain-Reaction (rRT-PCR)

For initial diagnostic and follow-up testing for COVID-19, there are varied specimen options for analysis. The CDC recommends collecting and testing upper respiratory (nasopharyngeal and oropharyngeal (if possible) swabs), and lower respiratory (sputum, if possible) for those subjects with productive coughs. Induced sputum may be collected if institutional practice allows. Testing may also be performed on blood (serum) samples. Institutional practices for the collection procedures and appropriate precautionary practices for avoiding transmission must be followed at all times.

For intubated subjects, endotracheal aspirate should be collected as outlined in the Table of Events.

Refrigerate specimen at 2-8°C until testing can be performed. Samples for screening should be prioritized on for testing as the results are required in order to intervene in a timely manner.

Note: Baseline testing for the detection of SARS-CoV-2 to confirm eligibility should be performed using rRT-PCR or other approved test based on institutional practice. All subsequent testing for the detection of SARS-CoV-2 should be performed by rRT-PCR.

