12.1.12.1.4. Endotracheal Aspirate

Endotracheal aspirate should be collected for intubated subjects only as outlined in Table of Events, [Section 7, Table 3](#). Sample should be collected per institutional practice. Samples should be labeled accurately.

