4.2 Missing Data

For time to event data in the efficacy analysis, if the subject withdraws after randomization but before any measurement, the subject will be censored at the randomization date. For subjects who have an

early termination or death, the censoring rule will be described in the corresponding section for each outcome.

For the event rate data in the efficacy analysis, last observation carry-forward (LOCF) will be used if applicable.

The outcomes for safety assessment and assessment additional to efficacy analysis will not be imputed if data is missing.

Please refer to corresponding sections in this SAP for more detail about missing data handling.

Additional rules for imputation of missing data may be determined during blinded review of the data and documented prior to unblinding.

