5.3 Blinded Data Review

Prior to scheduled unblinding and final data cleaning, the data may be reviewed in a blinded fashion. Based on analysis needs, the lead statistician will develop specific listings for this review and will document the sponsor or stakeholders' decisions prior to unblinding. [REDACTED]

[REDACTED] Blinded data review may also include clinical evaluation of safety data for reasonableness or to issue clinical queries to the site if needed. Any decisions affecting analysis will be described in internal documentation and the CSR.

6. Study Size and Power

Phase I Study

Fourteen (14) subjects will be treated with CYNK-001 in the Phase I portion. This sample size is determined to be adequate for the evaluation of safety and potential efficacy, based on clinical

judgement for this coronavirus disease and the current treatment status before starting Phase II portion. This number is not driven by hypothesis testing and power calculation.

Phase II Study

The primary efficacy endpoint is time to clinical improvement on the Ordinal Scale for Clinical Improvement (OSCI) defined by the World Health Organization (WHO), at Day 15. As preliminary purpose of proof of concept, without relevant data for the new coronavirus disease, no multiplicity will be adjusted and a 1-sided α of 0.05 will be used for the sample size consideration. With a sample size of 36 for each group (72 in total with 1:1 randomization ratio), a reduction of 50% for the time to event efficacy of CYNK-001 comparing with control can be detected with a power of at least 81% (assuming the time to clinical improvement is 8 days or earlier for CYNK-001 group, and 16 days or earlier for the control group with the same reduction rate of 50%) by using Log-rank test. This estimation is based on the study design with endpoint assessment at 28 days after infusion for each subject.

7. Analysis Populations

- Screened population – include the subjects who are screened.
- Safety Population – include all subjects who receive any amount of CYNK-001 in either phase or who enroll into the control group in phase II. Subjects will be analyzed according to the actual treatment they received for safety analysis.
- ITT Population– the definition of intent-to-treat population applies to phase II only. This population includes all randomized subjects. The subject will be analyzed according to the treatment arm they are randomized to.

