13.3 Analysis Methods

The primary endpoints will be analyzed with hypothesis testing procedures. No formal hypothesis will be carried out for secondary endpoints and the p-values are provided for informative purpose only.

Missing data and censoring will be handled as described below.

- **Primary Efficacy Analysis**

Phase II efficacy data will be analyzed for the ITT population based on randomized treatment group.

The primary efficacy endpoint is the time to clinical improvement on or before Day 28. Kaplan-Meier estimates of the survival curve, estimate of median survival time and its 95% CI will be calculated. Log-rank test will be used to test the difference between treatment groups while adjusting for pre-defined age strata.

Hazard ratio will be estimated via proportional hazard model using treatment as a factor stratified by age group.

Subjects who withdraw after randomization and before any measurements assessed will be censored at randomization date; subjects who terminate from the study before Day 28 without clinical improvement will be censored on the date of the last visit; and subjects who died without clinical improvement by OSCI will be censored on Day 28; subjects without clinical improvement ~~who have no event~~ on or before Day 28 will be censored on Day 28.

- **Secondary Endpoints Analyses**

The analysis will be based on the ITT population unless otherwise specified. Since the purpose of the analysis is for hypothesis generation, no multiplicity adjustment or adjustments for stratification covariates (age and site strata) will be made.

For the endpoints of event rate, including:

- Proportion of subjects who achieved clinical improvements by OSCI

- Proportion of subjects with clearance of SARS-CoV-2 by rRT-PCR
- Proportion of subjects who had pulmonary clearance by LRT specimens where it has previously been found
- Proportion of subjects who need invasive or non-invasive ventilation
- Proportion of subjects who died

The proportions and their two-side 95% CIs will be calculated. Fisher's exact test will be used to test the difference between treatment groups. If the subject has no data after baseline, the subject will be considered as failure in the analysis.

For endpoints of time to event, including:

- Time to clinical improvement measured by NEWS2 Score
- Time to clearance of SARS-CoV-2 by rRT-PCR testing
- Time to disappearance of virus from LRTI specimen
- Time from randomization to medical discharge

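### The Phase II pulmonary-clearance rate is taken over all randomised subjects, including those with no lower-respiratory virus to clear or no later specimen, so it is diluted and can be biased

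*SAP*

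**What the plan says.** **Analysis set and scoring.** For secondary endpoints SAP 13.3 states: "The analysis will be based on the ITT population unless otherwise specified". SAP section 7 defines ITT for Phase II: "This population includes all randomized subjects". The event-rate list in SAP 13.3 includes "Proportion of subjects who had pulmonary clearance by LRT specimens where it has previously been found". After that list, for all five rates together, comes the rule "If the subject has no data after baseline, the subject will be considered as failure in the analysis", with Fisher's exact test between arms. SAP 4.2 adds: "For the event rate data in the efficacy analysis, last observation carry-forward (LOCF) will be used if applicable".

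**Endpoint definition.** SAP 13.2 (item 10), protocol Table 2 and protocol 6.9 define the rate as a proportion of subjects and name no restricted denominator. SAP 13.2 does name subsets elsewhere: subjects requiring supplemental oxygen for oxygen-free days (item 12), and subjects admitted to the ICU for SOFA (item 14). For time to pulmonary clearance, protocol 6.9 censors everyone without clearance at Day 28.

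**Specimens.** Sputum is optional (protocol 6.1.2 and 12.1.12.1.2). Protocol 12.1.12.1 describes it as "lower respiratory (sputum, if possible) for those subjects with productive coughs", and permits induced sputum if the institution's practice allows. The endpoint definitions name induced sputum and endotracheal aspirate, each if available. On aspirate, protocol 12.1.12.1.4 says: "Endotracheal aspirate should be collected for intubated subjects only". Exclusion criterion 1 in protocol 8.2 reads: "Subject requires supplemental oxygen delivered by mechanical ventilation, either invasive or bilevel positive airway pressure".

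**The concern.** Clearance can be shown only in someone whose LRT specimen was positive and who later gives another. Neither condition is guaranteed, and the second can depend on how the patient fares. Sputum is sought from those with a productive cough, and an aspirate exists only after deterioration to intubation, because ventilated patients cannot enter. The analysis set and the scoring rule take no account of this.

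Three consequences follow:

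- A subject never LRT-positive has nothing to clear but stays in the denominator as not cleared.
- A baseline-positive subject with no later specimen can be scored a failure, either by the no-data rule or by carrying the positive result forward.
- A subject intubated after entry can become evaluable, and succeeds if a positive aspirate later turns negative.

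At stake is the meaning of the rate and of the difference between arms. The rate mixes virological clearance with availability of specimens, and availability may differ by arm for reasons related to treatment.

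**Working it through.** **1. Figures in the plan.** Neither document gives a sampling, positivity or clearance rate for LRT specimens. The only design figure that can be recomputed is power for the primary endpoint. Reading 8 and 16 days as exponential medians with 28 days of follow-up, the event probabilities are 1 − 2^(−28/8) = 0.912 and 1 − 2^(−28/16) = 0.703, so 36 × (0.912 + 0.703) = 58.1 events. Freedman's formula gives Φ(√58.1 × 1/3 − 1.645) = 81.5%, in line with the stated 81% or more at one-sided 0.05. It has no bearing on pulmonary clearance. The rest of this working uses assumed inputs; only the 36 per arm comes from the plan.

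**2. Ceiling and dilution.** Let e be the share of randomised subjects with a positive LRT specimen and a later one, and c the clearance proportion among them. With everyone else counted as not cleared, the ITT rate is e × c and cannot exceed e. Take true clearance of 70% versus 90%, the same e in both arms, two-sided 0.05, and the normal approximation for two proportions:

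| e | ITT rates shown | Power, ITT (36 per arm) | Power, evaluable only (36e per arm) |
|---|---|---|---|
| 0.25 | 17.5% vs 22.5% | 7.6% | 17.6% |
| 0.50 | 35% vs 45% | 13.6% | 31.7% |
| 0.75 | 52.5% vs 67.5% | 25.2% | 45.0% |
| 1.00 | 70% vs 90% | 56.6% | 56.6% |

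The dilution needs no difference between arms in sampling.

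**3. Bias from unequal specimen loss.** Assume 12 of 36 per arm are LRT-positive at baseline, with true clearance 9/12 (75%) on CYNK-001 and 6/12 (50%) on control. The ceiling is 12/36 = 33%.

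- Equal loss of one third of the clearers: (9 − 3)/36 = 6/36 (16.7%) versus (6 − 2)/36 = 4/36 (11.1%). The direction is kept, and the difference shrinks from 25 to 5.6 percentage points.
- Unequal loss, 6 of 9 versus 2 of 6: 3/36 (8.3%) versus 4/36 (11.1%). The direction reverses, by one subject.

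**4. A second illustration, with sampling tied to clinical course.** Assume every subject has LRT virus previously found. On CYNK-001, 80% recover, 5% are intubated and 15% remain ill; on control, 60%, 20% and 20%. Clearance is 95% if recovered and 40% otherwise. All intubated subjects and half of those still ill are resampled, and a share q of recovered subjects is resampled.

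- True clearance: 0.80 × 0.95 + 0.20 × 0.40 = 84% versus 0.60 × 0.95 + 0.40 × 0.40 = 73%.
- ITT rate, CYNK-001: 0.15 × 0.5 × 0.4 + 0.05 × 0.4 + 0.80 × 0.95 × q = 0.05 + 0.76q.
- ITT rate, control: 0.20 × 0.5 × 0.4 + 0.20 × 0.4 + 0.60 × 0.95 × q = 0.12 + 0.57q.

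| q | ITT rates, CYNK-001 vs control | Among resampled subjects only |
|---|---|---|
| 0 | 5.0% vs 12.0% | 40.0% vs 40.0% |
| 0.10 | 12.6% vs 17.7% | 61.5% vs 49.2% |
| 0.25 | 24.0% vs 26.3% | 73.8% vs 58.3% |
| 0.50 | 43.0% vs 40.5% | 81.9% vs 67.5% |
| 1.00 | 81.0% vs 69.0% | 87.6% vs 76.7% |

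The two ITT lines cross at q = 0.07/0.19 = 0.37. Below that the sign is wrong, and above it right. Which side the trial would have fallen on cannot be known from the documents.

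**The case against.** **The endpoint wording already limits the denominator.** It refers to specimens in which virus was found before, and ITT holds only unless something else is specified. This is a possible reading, but neither document turns the phrase into an analysis set, while SAP 13.2 does name subsets for other endpoints. Even on this reading, a baseline-positive subject with no later specimen can still be scored a failure.

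**The no-data rule may mean no data of any kind**, such as early withdrawal. That is possible, since one sentence serves five different rates. A subject with swabs but no later sputum then falls to LOCF, if that is held to apply, or has no rule. Hence such a subject can be scored a failure; it is not certain.

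**An intubated subject who clears has truly cleared.** That stands, and ventilation and death are captured by other endpoints. The difficulty is that deterioration creates the opportunity to be counted.

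**Stronger readings that the documents do not support.** A reader might infer that recovered subjects fail as a rule, so that an effective treatment lowers its own score and the test points the wrong way. The documents do not say that sputum ceases with recovery; this is an inference from its link to productive cough. Induced sputum may supply a specimen, and a recovered subject with a later negative specimen succeeds. Reversal appears only under the unequal loss chosen in the illustrations. A reader might also extend the no-data rule to time to pulmonary clearance; that rule governs the rates only.

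**Weight.** SAP 13.3 makes the secondary p-values informative only. SAP section 15 reports closure after 7 Phase I subjects, and its reduced analysis list omits pulmonary clearance. Both points stand and limit the importance of the finding.

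**Conclusion.** The concern holds as a flaw of the Phase II plan. Taken over all randomised subjects, the rate is capped at the share who are LRT-positive and resampled, and the arm comparison is diluted. That follows from the ITT denominator, unless the endpoint wording is read as an unstated restriction. The comparison can also be biased, because whether a later specimen exists can depend on clinical course and its absence can be scored as failure. How large the bias would be, and in which direction, cannot be determined: every sampling and clearance figure used above is an assumption, and sign reversal is possible but not shown to be likely. The LRT sampling days could not be checked, because most of the Table of Events is missing from the available copy; that gap is not a fault of the plan. The endpoint is secondary and informative, and no reported result is affected. The point matters if the Phase II plan is reused.

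**What to change.** In SAP 13.3:

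- Analyse the pulmonary-clearance rate in subjects with an rRT-PCR-positive LRT specimen at baseline. Specimens first positive after randomisation should not create evaluable subjects.
- Report three categories per arm: cleared, still positive, and no later specimen. Do not score the third as failure or fill it with a carried-forward positive.
- Show the number evaluable per arm beside each rate.
- Use the same baseline-positive set for time to pulmonary clearance, where subjects with nothing to clear would otherwise be censored at Day 28.

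The cost is a few sentences in the SAP and one field for the reason a specimen was not obtained. The price in precision is a smaller set and a wider interval. Restriction at baseline does not remove the dependence of resampling on clinical course; the separate category makes it visible. In the second illustration, among resampled subjects only, the true advantage disappears when no recovered subject is resampled (40.0% in both arms).

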13.1 Primary Efficacy Endpoint

13.1.1 Primary Efficacy Endpoint for Phase I

The efficacy analysis for Phase I will be based on the safety analysis population.

The primary efficacy endpoint for Phase I is clinical improvement by OSCI on or prior to Day 15. Clinical improvement by OSCI is defined as at least one patient state improvement compared to baseline. If clinical improvement by OSCI is demonstrated for at least 2 out of 14 subjects on or prior to Study Day 15, and CYNK-001 is deemed to be safe, the study will move to Phase II. Otherwise, the study will be terminated.

Phase I efficacy data will be summarized by descriptive analyses for the number and proportion of subjects who achieved clinical improvement by OSCI by Day 15.

The proportion of the clinical improvement by OSCI at Day 15 will be summarized with a point estimate, standard error and a 95% confidence interval.

Patients who do not achieve at least one patient state improvement will be considered as failure to improve by OSCI. No formal hypothesis testing will be carried out for this part of the analysis.

Subject listings of clinical status using OSCI will be provided.

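### One rule, that no post-baseline data means failure, also covers the death and ventilation rates, where it yields an unobserved and undetermined outcome

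*SAP*

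**What the plan says.** In the secondary analyses of SAP 13.3, five event rates form one list. Three are favourable: OSCI improvement ("Proportion of subjects who achieved clinical improvements by OSCI"), SARS-CoV-2 clearance and pulmonary clearance. Two are harmful: "Proportion of subjects who need invasive or non-invasive ventilation" and "Proportion of subjects who died". All five get a proportion, a two-sided 95% interval and the same test: "Fisher's exact test will be used to test the difference between treatment groups". The missing-data rule follows directly, with no exception for any endpoint: "If the subject has no data after baseline, the subject will be considered as failure in the analysis".

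Other places that bear on it:

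- SAP 4.2 gives a general rule: "For the event rate data in the efficacy analysis, last observation carry-forward (LOCF) will be used if applicable". It refers the reader to later sections for detail and allows more imputation rules to be set at blinded review.
- SAP 13.1.1, for Phase I, is the one place that spells out what a failure is: "Patients who do not achieve at least one patient state improvement will be considered as failure to improve by OSCI".
- SAP 13.3 repeats the no-data rule for the NEWS2 improvement rate. It also restates the mortality comparison, there with no missing-data rule.
- Protocol 8.2 excludes at entry: "Subject requires supplemental oxygen delivered by mechanical ventilation, either invasive or bilevel positive airway pressure".

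**The concern.** For improvement and clearance, treating a subject without data as a failure is a familiar conservative convention: the benefit is not credited. For death and ventilation the bad outcome is the event itself, so the same sentence either creates an event that nobody saw or, read the other way, records its absence without evidence.

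The plan foresees the subjects concerned. Randomisation is placed at screening in the Protocol's Table of Events, before Day 1. The ITT population keeps everyone randomised, subjects are not replaced (Protocol 14.9), and SAP 4.2 and 13.3 both provide for withdrawal after randomisation but before any measurement. The primary analysis censors such a subject at randomisation, whereas the mortality table may count a death.

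At stake are the reported rates and intervals for all-cause mortality and ventilation. Two programmers following the SAP could report different mortality from the same data.

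**Working it through.** **Step 1. What each reading does to an ITT subject with no post-baseline data.**

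| Rate | Failure = bad outcome | Failure = event not achieved | LOCF from baseline |
|---|---|---|---|
| OSCI improvement | not improved | not improved | not improved |
| Viral or pulmonary clearance | not cleared | not cleared | not cleared |
| Ventilation | **ventilated** | not ventilated | not ventilated (excluded at entry, Protocol 8.2) |
| Death | **dead** | alive | alive |

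The readings agree for the favourable rates and conflict only for the two harmful ones. LOCF from baseline is itself a reading: SAP 4.2 does not say whether a baseline value may be carried forward.

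**Step 2. Inputs.** The plan gives no death, ventilation or withdrawal rate for this trial. Protocol 6.7 mentions a drop-out assumption without a figure. The only design number needed is 36 per arm (Protocol synopsis, SAP 6). The power statement behind it reproduces, assuming exponential times with medians of 8 and 16 days and 28 days of follow-up:

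- Event probabilities are 0.912 and 0.703, so expected events are 36 × (0.912 + 0.703) = 58.1.
- Freedman's formula, one-sided 0.05: Φ(√58.1 × 0.5/1.5 − 1.645) = 81.5%, against a stated figure of at least 81%.

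This confirms the arm size and has no other bearing on the point.

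Assumed true deaths are 2 or 4 per arm (5.6% or 11.1%). They are set near the 4.3% and 11% in two hospital cohorts described in Protocol 4.1, which included ICU patients and are only a rough guide here. Assumed no-data subjects are 0, 2 or 4 per arm.

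**Step 3. Size on the ordinary reading.** Tabulated rate = (true deaths + no-data subjects)/36. Each no-data subject adds 1/36 = 2.8 points, and the same increment applies to ventilation.

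| True deaths, CYNK-001 v control | No-data subjects, CYNK-001 v control | Tabulated mortality | Fisher p, two-sided |
|---|---|---|---|
| 2 v 2 | 0 v 0 | 5.6% v 5.6% | 1.0 |
| 2 v 2 | 2 v 2 | 11.1% v 11.1% | 1.0 |
| 4 v 4 | 2 v 2 | 16.7% v 16.7% | 1.0 |
| 2 v 2 | 0 v 2 | 5.6% v 11.1% | 0.67 |
| 2 v 2 | 0 v 4 | 5.6% v 16.7% | 0.26 |
| 4 v 4 | 0 v 2 | 11.1% v 16.7% | 0.74 |
| 4 v 4 | 0 v 4 | 11.1% v 22.2% | 0.34 |

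With equal withdrawal both rates are inflated and the comparison is not biased. With no true difference, a nominal p below 0.05 needs 7 control-only no-data subjects at 2 v 2 deaths (7/36 = 19.4% of the arm; p = 0.046) and 8 at 4 v 4 (8/36 = 22.2%; p = 0.045).

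**Step 4. The other readings, same data.** With 4 v 4 deaths and 4 control-only no-data subjects, event not achieved gives 11.1% v 11.1% (p = 1.0). Leaving those subjects out gives 4/36 = 11.1% v 4/32 = 12.5% (p = 1.0). The control figure is therefore 11.1%, 12.5% or 22.2%, depending on a choice the SAP does not make.

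**The case against.** The best defence is that *failure* in this SAP elsewhere refers to a benefit not achieved: no OSCI improvement in 13.1.1, no NEWS2 improvement in 13.3. On that usage the subject counts as alive and unventilated, and no events are invented. This is a fair reading, and it rules out saying that the plan definitely scores withdrawals as deaths. It does not repair the plan, because alive and unventilated is equally unobserved.

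SAP 4.2 applies LOCF only where applicable and points to later sections, so 13.3 may be meant to override it. If so, that settles precedence for subjects with no data, but not what *failure* means. Nor may one state as a rule of the plan that a subject seen once is carried as alive to Month 6. The text permits this but does not prescribe it.

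The trigger is narrow. OSCI is recorded daily in hospital and by phone for outpatients (Protocol 11), so few subjects may have no data at all. The p-values are for information only, and the primary analysis is untouched. SAP 15 records closure after 7 Phase I subjects, with a list of deaths but no arm-level mortality or ventilation rate among the remaining outputs. All of this stands and limits the consequence.

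A reader might infer that the rule makes the open-label control arm look worse and so favours CYNK-001. The documents do not support that. Nothing in them says that control subjects withdraw more often or sooner, and no withdrawal rate is given for either arm. It is possible in an open-label trial, but it is an assumption.

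**Conclusion.** The point holds as a defect of the written Phase II plan. A rule suited to favourable endpoints is applied without exception to death and ventilation, where it gives either an invented event or an assumed non-event, with no stated precedence over LOCF. On the ordinary reading the inflation is 2.8 points per affected subject per arm. Two such subjects double a 2/36 death rate. This rests on 36 per arm and on assumed counts, since the documents give no rate of subjects without post-baseline data.

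Bias between arms is conditional on unequal withdrawal and is not shown. The damage is to descriptive secondary rates and their confidence intervals. No reported comparison is affected, because Phase II was not run.

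**What to change.** In SAP 13.3, define the missing-data outcome by endpoint:

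- Keep the no-data-is-failure rule for the favourable endpoints only: OSCI and NEWS2 improvement, viral clearance and pulmonary clearance.
- For death and ventilation, impute no event. Use known vital and ventilation status, do not carry alive forward by LOCF to Day 28 or Month 6, and report by arm how many subjects have unknown status.
- Show best-case and worst-case counts as sensitivity analyses. For 2 deaths and 2 unknown in an arm these are 2/36 = 5.6% and 4/36 = 11.1%.
- State in SAP 4.2 that the endpoint-specific rules take precedence over LOCF.

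A Kaplan-Meier mortality estimate censored at the last date known alive is a reasonable option, though it assumes uninformative withdrawal. The Protocol defines mortality as a proportion, so it is not essential, and a competing-risk analysis of ventilation is not required.

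The cost is a few sentences of SAP text and two extra tabulations. No new data are needed: OSCI, procedures and reasons for discontinuation are already collected. With the trial closed, the change matters mainly if this text is reused.
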